- Serum specimens will be collected at each study visit and 4 weeks after the last dose from all subjects only in part 2.
- Data collection will be by conventional paper case report forms (CRF's).

Sample size considerations

During the first phase of the study (immunization of children 2-4 years of age), the outcome of interest is reactogenicity. Even if intussusception were to occur with a relative risk similar to that observed with RRV-TV, we do not expect to observe intussusception with the small numbers included in this Phase I study. We will however use fever as a measure of reactogenicity. Based on previous studies in the USA involving active surveillance, we expect a background rate of 5% of fever (among placebo recipients). With 90 subjects (30 with $10^{5.0}$ ffu, 30 with $10^{6.0}$ ffu and 30 placebo), we will have 80% power ($p=0.05$) to detect a 35% incidence of fever among vaccinated subjects (assuming a background rate of 5% among controls). The same sample size assumptions hold true for the infant study.

For the second part involving both safety and immunogenicity, the primary outcome measure of interest is immunogenicity, although through this and all subsequent studies, reactogenicity will continue to be monitored. With 136 vaccinees in each vaccine group ($10^{5.0}$ 2 doses, $10^{5.0}$ 3 dose, $10^{6.0}$ ffu 2 doses) and 68 subjects receiving placebo, we will be able to detect a difference in take rates of 15% between the two dose levels (70% vs. 85%). The sample size will be sufficient to detect a difference in take rates of 12% (75% vs. 87%) between 2 doses of $10^{5.0}$ ffu and $10^{6.0}$ ffu. We are also assuming that 35% of infants will be exposed to wild type rotavirus during the 8 week study period and our numbers will be sufficient to differentiate a take rate between vaccine responses and background responses. If the proportion among controls is actually lower, and 70% of children have a four-fold rise in serum antibody titer, then the number of subjects required to achieve significance will be lower.

Study Cohort

Numbers of subjects / centres: Field workers will identify children of appropriate age, inform families of the purpose and scope of the study and offer participation. It is planned to vaccinate 10-12 children daily, and first dose of vaccines are expected to be complete within 2 weeks of the start of the study.

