- On day 42, insure that all concomitant medication taken during the study have been recorded.

Day 43 to 6 months.

- Monthly active surveillance to complete 6 months of followup. With each visit, inquire about symptoms or illnesses among subjects.
- At end of 6 months, terminate subject from the study

For infants(Part 2)

Day 0 (Visit 1)

- Same procedures as performed for toddlers in part 1.
- Obtain a blood sample for serology
- Prepare study vaccine and administer dose 1
- Collection of stool sample for rotavirus antigen by ELISA

Day 3, 7, 14, and 21 (first 150 subjects only)

- Collection of stool sample for rotavirus antigen by ELISA

Day 1-day 27

- Carry out active surveillance with all subjects by visiting house daily for 2 weeks and thereafter twice weekly. Measure rectal temperature daily. Use daily form to record symptoms or lack of symptoms. Have physician available at clinic and inform family of subjects that the physician is available should there be any illness during the time of the study. If subjects are brought to the clinic, record all symptoms in patient medical records. These medical records will be the source documents for the passive surveillance.

Day 28

- Insure that subject is eligible for dose 2 according to inclusion and exclusion criteria
- Obtain a serum blood sample for serology
- Prepare study vaccine and administer dose 2
- Collection of stool sample from subjects (first 150 only) for rotavirus antigen by ELISA

Day 29 – day 42

- Carry out active surveillance with all subjects by visiting house daily for 2 weeks. Measure rectal temperature daily. Use daily form to record symptoms or lack of symptoms. Have physician available at clinic and inform family of subjects that the physician is available should there be any illness during the time of the study. If subjects are brought to the clinic, record all symptoms in patient medical records. These medical records will be the source documents for the passive surveillance.

Day 31, 35, 42, 49 (first 150 subjects only)

- Collection of stool sample for rotavirus antigen by ELISA

Day 43-day 55

- Twice weekly active surveillance inquiring about symptoms or illnesses among subjects.

Day 56

- Insure that subject is eligible for dose 3 according to inclusion and exclusion criteria

- Obtain a serum blood sample for serology
 - Prepare study vaccine and administer dose 3
 - Collection of stool sample from subjects (first 150) for rotavirus antigen by ELISA
- Day 57-day 70

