Baseline characteristics of the subjects receiving vaccine and placebo will be examined for group comparability. Any significant baseline differences will be controlled for during data analysis. The frequency distribution will be examined to assess the distribution of data. Proportion of infants with adverse events will be compared between the different groups (vaccine, placebo, different doses and viral concentrations). Proportion of subjects that shed rotavirus at different time periods will be compared. Serological measures (proportion with ≥ 4 -fold increase in titer and geometric mean titer) will be compared between different viral concentrations/ doses and placebo recipients.

The proportions will be compared using χ^2 -tests and rate ratios (95% confidence intervals). The geometric mean titers (GMT) will be compared using non-parametric tests. Multivariate analysis will be done to simultaneously adjust for different factors.

Ethical Assurance for Protection of Human Rights

Describe in the space provided the justifications for conducting this research in human subjects. If the study needs observations on sick individuals, provide sufficient reasons for using them. Indicate how subject's rights are protected and if there is any benefit or risk to each subject of the study.

Human rotavirus vaccine (RIX4414), designed for preventing rotavirus will be evaluated among young children since the risk of the disease is greatest in that age group. Infants will be enrolled after their parents have been given a full explanation of the study and they have understood the implications of participating in this study, and have agreed to participate in writing. The study will be conducted according to Good Clinical Practices, the Declaration of Helsinki, and local rules and regulations of Bangladesh and the ICDDR,B.

The investigator and his staff will be aware of the possible increased risk of intussusception and will consider this diagnosis among children presenting symptoms of intussusception. The investigator and his staff will take appropriate actions to evaluate and treat the condition. A child with suspected intussusception will be referred to a local hospital in Dhaka (Children's hospital, Shishu Hospital). The hospital has the experience and capacity for diagnosis, non-surgical and surgical management of intussusception, and a pediatric surgeon at this hospital is a co-investigator on the protocol to assume

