5. We have recalculated the sample size and accordingly changed the design of the protocol. We feel strongly the necessity to test its candidate vaccine at different viral concentration and at different dose schedules. Moreover, there is evidence in the literature of a rather high attack rate of human rotavirus in Bangladesh between 20 to 30% of children that are hospitalized with diarrhea are infected with rotavirus (Albert et al, J Clin Microbiol. 1999; 37:3458-64. Kilgore, et al. Pediatric Infect Dis J 1996, 15:672-7. Haque et al, J Trop Pediatr. 1994 40:351-4). Previous trials conducted with Rotashield in Bangladesh demonstrated that 75% of vaccinees (aged 6-14 weeks) had a 4-fold or greater rise in IgA titer (unpublished result). We have considered this for the calculation of our sample size.

The outcome of this trial in Bangladesh will provide the information necessary to decide the appropriate viral concentration and dose regimen for testing of the HRV vaccine efficacy and safety in the large phase III trial.

With regards to the fevers, the AVANT uncloned P33 89-12 vaccine candidate was shown to be safe in US infants (Bernstein et al, 1998, Bernstein et al, 1999). After administration of the first dose of 10^5 ffu of uncloned P33 89-12, 19 % of the infants had mild fever as compared to 5% of the infants that received the placebo. The Rota-003 trial (Finland study, phase II, double blind, randomized placebo-controlled trial, unpublished) conducted with the GSK cloned RIX4414 candidate vaccine has confirmed the observed safe reactogenicity profile. None of the subjects that received the 10^5 ffu RIX4414 vaccine or placebo had fever after dose 1. Only one of the subjects that received the 10^6 ffu RIX4414 vaccine had fever after dose 1 and one of the subjects that received placebo. It can be concluded that there is no increase in fevers as observed due to the use of a higher viral concentration.

6. An improved study design is outlined in our revised version.

7. For phase II studies, inclusion and exclusion criteria are quite stringent and these have been spelled out clearly (page 16 and 17). **Annex III** (page 46) provides the composition of the vaccine. Any known

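### The 12-point take-rate claim (75% vs 87%) at 136 per group has about 72% power two-sided, and reaches 80% only with a one-sided test that the protocol does not state

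*Protocol*

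**What the plan says.** The Part 2 paragraph of Sample size considerations makes two statements about take rates with 136 infants per vaccine group. The first is "we will be able to detect a difference in take rates of 15% between the two dose levels (70% vs. 85"%). The second, on the lower against the higher viral concentration, is "The sample size will be sufficient to detect a difference in take rates of 12% (75% vs. 87%) between 2 doses of" each. Neither gives a power, a significance level or a sidedness.

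The one explicit convention in the section belongs to the Part 1 fever comparison: "we will have 80% power ($p=0.05$) to detect a 35% incidence of fever among vaccinated subjects". The sentence that closes the fever paragraph says that the same assumptions apply to the infant study. It does not say whether that covers only fever in infants or the take-rate comparison as well.

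The Data Analysis section says: "The proportions will be compared using χ^2 -tests and rate ratios (95% confidence intervals"). Sidedness is not mentioned there or elsewhere.

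The 75% starting rate has a local source, given in the response to the external reviewers' comments (second reviewer, point 5): "Previous trials conducted with Rotashield in Bangladesh demonstrated that 75% of vaccinees (aged 6-14 weeks) had a 4-fold or greater rise in IgA titer". The authors add that they used this figure in the sample size.

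**The concern.** The 12-point sentence is a flat statement of sufficiency. A reader who applies the section's 80% power and p=0.05, and takes the chi-square tests and 95% confidence intervals as two-sided in the usual way, will believe that a 12-point advantage of the higher concentration would be found four times in five. On that reading it would not.

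This comparison matters for the next step. In the response to the external reviewers' comments the authors write: "The outcome of this trial in Bangladesh will provide the information necessary to decide the appropriate viral concentration and dose regimen" for the Phase III trial. It also starts from the take rate seen locally with an earlier rotavirus vaccine, so of the two stated scenarios it is the one tied to local data. If the power is overstated, a non-significant difference would be taken as stronger evidence against the 10^6 concentration than it is.

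**Working it through.** **Inputs.** Take rates 75% and 87%, and 70% and 85% (Sample size considerations). 136 infants per vaccine group, allocated 1:1 between the groups compared (Sample size considerations; the Part 2 design table gives 2:2:2:1). Power 80% and p=0.05 (fever paragraph). Two-sided testing is inferred from the chi-square tests and 95% confidence intervals in Data Analysis. No allowance for loss is stated, so zero loss is assumed first.

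**Formula.** For two proportions with n per group and mean rate p̄:

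- SE0 = √(2·p̄(1−p̄)/n)
- SE1 = √((p1(1−p1) + p2(1−p2))/n)
- power = Φ((d − z·SE0)/SE1), with z = 1.96 two-sided and 1.645 one-sided.

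**Companion claim, 70% vs 85%.** p̄ = 0.775, SE0 = √(0.34875/136) = 0.0506, SE1 = √(0.3375/136) = 0.0498. Two-sided power = Φ((0.15 − 1.96 × 0.0506)/0.0498) = 0.846. For 80% power, 121 per group are needed (134 with continuity correction). The claim holds at 136.

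**Disputed claim, 75% vs 87%, two-sided.** p̄ = 0.81, SE0 = √(0.3078/136) = 0.0476, SE1 = √(0.3006/136) = 0.0470. Power = Φ((0.12 − 1.96 × 0.0476)/0.0470) = Φ(0.57) = 0.715. Exact enumeration of the uncorrected chi-square test gives 0.724, and with continuity correction 0.664.

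**Sample size for 80% power, two-sided.** n = (1.96·√0.3078 + 0.842·√0.3006)²/0.12² ≈ 2.40/0.0144, which rounds up to 167 per group (183 with continuity correction).

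**Can the figure of 136 be reproduced for 75% vs 87%?** Yes, with a one-sided 5% test and no correction. Power = Φ((0.12 − 1.645 × 0.0476)/0.0470) = 0.813, and 80% power needs 132 per group.

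**Detectable difference at 136 per group.** Starting from 75% and solving for 80% two-sided power gives about 88.1%, a difference of about 13.1 points.

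**All claims in the section on each basis (per group, 80% power, 5%, uncorrected).**

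| Claim | Planned | Two-sided | One-sided |
|---|---|---|---|
| Fever, 5% vs 35% | 30 | 27 | 21 |
| Take, 70% vs 85% | 136 | 121 | 95 |
| Take, 75% vs 87% | 136 | 167 | 132 |

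**Loss of evaluable infants (assumed range).** With 5%, 10% or 15% loss, two-sided power for 75% vs 87% falls from 71.5% to 69.3%, 66.9% or 64.4%.

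**The case against.** The strongest reply is that the sentence promises no particular power. The 80% and p=0.05 are attached to fever, sidedness is open, and a one-sided 5% test makes the sentence true at 81%. A directional question is plausible, because the background argues that a higher concentration may be needed in Bangladesh. This stands to the extent that the sentence is not wrong under every convention. It does not remove the problem: no one-sided test is stated, and chi-square tests with 95% confidence intervals point to two-sided testing.

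A second reply is that the consequence is small. The 15-point claim still holds at 136, both rates are planning values, the 75% comes from a different vaccine, and the planned confidence intervals and geometric mean titers will show more than one p-value. That is fair, and it limits the weight of the point.

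Three stronger readings are tempting, and the protocol does not support them.

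- A reader might infer that the two take-rate claims cannot rest on one convention, since 134 per group (two-sided, corrected) nearly matches 136 for the first and 183 is needed for the second. The table shows otherwise: a one-sided 5% test fits both, and the fever claim too. The two-sided corrected basis would itself need 34 per group for fever, where 30 are planned.
- A reader might say that the sentence leaves the comparison undefined. It does not; it names two doses at each concentration.
- A reader might look for a rescue by pooling both 10^5 groups on the day-56 serum, taken before dose 3 (272 vs 136, 82.3% power). The protocol plans no such pooling. It also depends on the two-dose groups receiving active vaccine on days 0 and 28, which is not stated, and power drops below 80% at about 6% loss.

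**Conclusion.** The claim that 136 per group suffices for 75% vs 87% is not delivered on the natural reading. Two-sided power is about 72%, so a true 12-point advantage would be missed about 28% of the time rather than 20%. The difference detectable with 80% power is about 13 points. This rests on carrying the section's 80% and p=0.05 over to Part 2, on reading the planned tests as two-sided, and on no loss of evaluable infants.

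The finding concerns one stated figure. It does not show that the trial is too small: the 15-point claim holds at about 85% power, and a one-sided 5% test would support the 12-point claim. The correction is nevertheless worth making, because the figure bears on the choice of concentration.

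**What to change.** Replace the 12% sentence with wording such as: *Two-sided 0.05, 136 vs 136, before any loss of evaluable infants: 80% power for 75% vs about 88% (about 13 points), and about 72% power for 75% vs 87%.* The 70% vs 85% statement can stay, with its two-sided power (about 85%) added.

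This adds no infants, visits or samples. The only cost is a slightly less favourable stated detectable difference.

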4. [name]	Virologist, Lab. Sciences Division	Co-investigator
5. [name]	Scientist, Clinical Sciences Division	Co-investigator
6. [name]	Paediatric Surgeon, Shishu Hospital, Dhaka	Co-investigator
7. [name] [name]	Head, Progrm. Infect Dis & Vaccine Scien.	Co-investigator
8. [name] [name]	Director, ICDDR,B	Co-investigator

DESCRIPTION OF THE RESEARCH PROJECT

Hypothesis to be tested:

Concisely list in order, in the space provided, the hypothesis to be tested and the Specific Aims of the proposed study. Provide the scientific basis of the hypothesis, critically examining the observations leading to the formulation of the hypothesis.

1. Human rotavirus vaccine (RIX4414) is safe and immunogenic in infants

Specific Aims:

Describe the specific aims of the proposed study. State the specific parameters, biological functions/ rates/ processes that will be assessed by specific methods (TYPE WITHIN LIMITS).

Part 1 (Safety assessment in toddlers)

Primary

- For each vaccine concentration (10^5 and 10^6 ffu), to assess the safety and reactogenicity of a single oral dose of the rotavirus vaccine *versus* placebo in healthy children 2-4 years old.

Secondary

- To assess viral shedding in each study group.

Part 2 (Safety and immunogenicity assessment in infants)

Primary

- To assess the immunogenicity of the rotavirus vaccine after any dose in the study vaccine groups (infants aged 6-14 weeks).

Secondary

- For each viral concentration, to assess the safety and reactogenicity of two/three oral doses of the rotavirus vaccine *versus* placebo.
- To assess viral shedding in a subset of subjects.

Background of the Project including Preliminary Observations

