Inclusion criteria for enrollment: Male or female, between 24 months and 48 months of age at the time of the first dose of vaccine for participation in the study part assessing the vaccine in toddlers. Male or female, between 6 and 14 weeks of age at the time of the first dose of vaccine for participation in the study part assessing the immunogenicity and safety of the vaccine in infants. Written informed consent, free of chronic or serious medical condition as determined by history and physical exam within 3 days of the first dose of vaccine, plan to stay in community for at least 3 months.

Exclusion criteria for enrollment: Malnutrition (<-2Z score weight for age), fever (>38°C), acute or chronic illness, use of antimicrobial drug within previous 14 days, hypersensitivity to any of the vaccine components (vaccine composition in **annex III**), use of any investigational drug during previous 30 days, any uncorrected congenital malformation of the gastrointestinal tract, use of any immunosuppressing drugs during the last 14 days (likelihood is remote), any evidence by physical exam of immunosuppressing condition, administration of gamma globulin or any other blood product, previous intussusception or abdominal surgery, known pregnant person in the home.

Elimination criteria during study: If an exclusion criteria develops while participating in the study, the subject will be eliminated from the study.

Definitions:

Fever: Rectal temperature > 38°C

Diarrhoea: Three or more looser stools than normal stools in a 24 hour period.

Contraindications to vaccination: Not applicable.

Conduct of the study: The study will be conducted according to Good Clinical Practices, the Declaration of Helsinki, and local rules and regulations of Bangladesh and the ICDDR,B. It will be reviewed and approved by the Ethical Review Committee (ERC) of the ICDDR,B prior to starting the study. The ERC is a recognized committee for review of research protocols involving humans and has a Multiple Project Assurance (MPA) with a US agency (USAID).

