Informed consent: The parents of the subjects will sign a consent form informing them of the nature of the study, its rationale, and its risks and benefits. The informed consent document will embody the elements of the consent as described in the Declaration of Helsinki, and the ICH Harmonized Tripartite Guidelines for Good Clinical Practices. The investigator or designate will describe the protocol to parents of potential subjects face to face. The subject information and consent form may be read to the parents of potential subjects, but in any event, the investigator will give the parents ample opportunity to inquire about the details of the study and ask questions before signing the consent form (**annex I**). The consent form will describe the possible side effects including the potential risk of IS. While the likelihood is extremely low of intussusception being temporally linked to participation in this small study, we will insure that health care workers are trained to recognize symptoms and clinical signs of intussusception—this is the principal reason for such aggressive, active surveillance for adverse events. We will have an arrangement with a local hospital (Children's hospital, Shishu Hospital in Dhaka) with experience and capacity for diagnosis, non-surgical and surgical management of intussusception. Any patient meeting a case-definition consistent with intussusception will be transported to the hospital for evaluation and treatment.

Total duration of follow-up after vaccination: According to recommendations of the European Committee for Proprietary Products (CPMP) all vaccinated children will be followed up for at least 6 months after the last immunization considering the safety issue (CPMP, 1999). Since the long-term follow up does not require any active surveillance for

the subjects, and since no efficacy end point is part of this protocol, active surveillance of diarrheal events will not be done.

The protocol will be reviewed for scientific quality by the Research Review Committee (RRC) of the ICDDR,B. The Research Review Committee (RRC, with 13 members), composed of clinicians, epidemiologists, social scientists, laboratory scientists, and demographers/population scientists from both within and outside the center, reviews all scientific research proposals of the center, evaluates their scientific merit, competence of Principal Investigators, and relevance to the Centre's objectives and priorities.

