hypersensitivity to any of the components should be a contraindication to vaccination. The use of immunosuppressing drugs is known to affect the immune response. Although the likelihood that such drugs are used at the targeted population is remote, we want to collect the data. If the mother or woman of the household were to become pregnant after an infant was enrolled and immunised, this child should be excluded for the administration of the next scheduled dose as there are no transmission data available.

8. We agree to the concern raised by the committee and will allow concomitant administration of OPV.

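### The elimination rule removes from the study any child who develops fever, acute illness or antimicrobial use after vaccination, contradicting the protocol's own follow-up of all vaccinated children

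*Protocol*

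**What the plan says.** The exclusion criteria for enrollment, in the Study Cohort section of the protocol, begin "Malnutrition (<-2Z score weight for age), fever (>38°C), acute or chronic illness, use of antimicrobial drug within previous 14 days" and later list previous intussusception. The next paragraph, on elimination during the study, states: "If an exclusion criteria develops while participating in the study, the subject will be eliminated from the study". It sets no time limit, exempts no event, and does not distinguish withholding a dose from ending participation.

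The Definitions that follow give "Fever: Rectal temperature > 38°C", the same threshold as the exclusion criterion. Sample size considerations say "We will however use fever as a measure of reactogenicity". The primary aim of Part 1 is "to assess the safety and reactogenicity of a single oral dose of the rotavirus vaccine" against placebo.

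Other parts of the protocol assume that children stay in:
- Total duration of follow-up after vaccination: "all vaccinated children will be followed up for at least 6 months after the last immunization".
- Outline of study procedures: home surveillance covers all subjects, and the criteria are checked again before doses 2 and 3.
- Follow-up of intussusception cases: acute and convalescent blood is taken from cases.
- Response to external Reviewers' comments, Reviewer # 2, item 7, on a pregnancy arising in the household: "this child should be excluded for the administration of the next scheduled dose".

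**The concern.** A child who meets the reactogenicity endpoint also meets the condition for elimination. Staying under observation then depends on a post-vaccination outcome.

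For an eliminated child the study loses later symptoms, any stool sample still due, and the rest of the six-month safety follow-up. In Part 2 it also loses reactogenicity after later doses and the later blood samples on which the primary immunogenicity outcome rests. Later-dose safety would be seen only in children who had no fever, illness or antimicrobial use earlier. If the vaccine raises fever, the loss differs by arm, and the serology comparison is no longer between the groups as randomised.

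**Working it through.** **1. The passages side by side.** Take a child with a rectal temperature above 38°C on day 3.
- Under the elimination paragraph the child leaves the study.
- Under the follow-up paragraph the child is followed for at least six months after the last dose.
- Under the visit outline the child is visited daily to day 14 and, if an infant, is assessed for the next dose at day 28.
- Under the reply in item 7 (given for household pregnancy), a new criterion affects only the next dose.

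These cannot all be followed. A child with intussusception meets a listed exclusion criterion, yet the intussusception annex requires later samples from that child.

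**2. The plan's own power figure for fever.** Inputs from Sample size considerations: 30 per group, 5% versus 35%, p = 0.05, stated power 80%. With p̄ the mean of the two rates, the pooled two-sided formula is

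Power = Φ{[|p1 − p2| − 1.96·√(2p̄(1 − p̄)/n)] / √([p1(1 − p1) + p2(1 − p2)]/n)}

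Here p̄ = 0.20, giving Φ[(0.300 − 0.202)/0.0957] = 84.6%. Two-sided Fisher exact power by enumeration is 78.8%. The stated 80% is reproduced, and it presumes that all 30 children per group are counted.

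**3. Loss per arm in Part 2.** Assumptions: fever only, and one constant, independent rate f per dose. The low value, 5%, is the protocol's background rate. The high value, 19%, is the parent-strain rate after dose 1 in US infants (response to Reviewer # 2, item 5). Children remaining after k doses = n(1 − f)^k.

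| Arm | f | After 1 dose | After 2 doses |
|---|---|---|---|
| Vaccine, 136 | 5% | 129.2 | 122.7 |
| Vaccine, 136 | 19% | 110.2 | 89.2 |
| Placebo, 68 | 5% | 64.6 | 61.4 |

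At 19% on vaccine and 5% on placebo, 0.81² = 66% and 0.95² = 90% remain after two doses. At equal rates there is no imbalance.

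**4. Power at the two-dose sizes.** Same formula, equal arms, both arms losing at the same rate. The contrasts are those in Sample size considerations.

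| n per arm | 75% vs 87% | 70% vs 85% |
|---|---|---|
| 136 (planned) | 71.5% | 84.6% |
| 123 (f = 5%) | 67.2% | 80.8% |
| 89 (f = 19%) | 53.2% | 67.1% |

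For 75% versus 87% at n = 136: p̄ = 0.81, Φ[(0.120 − 0.0932)/0.0470] = 71.5%. The rule costs about 4 to 18 points in either contrast (71.5 − 67.2 and 71.5 − 53.2; 84.6 − 80.8 and 84.6 − 67.1). The shortfall from 80% in the first contrast is there before any elimination. Acute illness and antimicrobial use would add losses that the documents do not allow to be sized.

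**The case against.** The strongest defence is that the rule was never meant literally. The list is headed as criteria for enrollment, eligibility is re-checked before each later dose, and the authors told a referee who queried this very rule that the child misses the next dose. That is a plausible account of intent. But a reply to a referee is not the operative text, which still says elimination from the study.

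A second defence is that analysis sets belong in the statistical analysis plan. That is fair for denominators. It does not cover a rule that stops data collection, because an analysis plan cannot restore visits and samples that were never made.

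The defence is right against several stronger readings that a reader might infer:
- **That the fever endpoint deletes its own cases.** Temperature is measured daily and symptoms go on a daily form, so the triggering fever is captured. Nothing says collected data are discarded, and Data Analysis names no denominator. A first-fever proportion survives if data before elimination are analysed.
- **That losses certainly fall more on vaccine arms.** Expected outcomes allows for a higher rate of mild temperature elevation, and the parent strain showed 19% versus 5%. But for RIX4414 itself, item 5 of the same response reports no fever at 10^5 ffu after dose 1, one case at 10^6 ffu, and none or one on placebo (it states both), without group sizes.
- **That 10.5 of 30 vaccinated toddlers (0.35 × 30) against 1.5 of 30 on placebo would go.** The 35% is the alternative in a power statement, not a forecast.
- **That 29% versus 8% leave after dose 1, by adding the Table 1 fever bands.** Table 1 does not label them as first-dose.
- **That intussusception cases go unobserved.** The main text and the annex require immediate reporting, safety board review and repeated sampling. This shows the contradiction, not an absence of follow-up.

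**Conclusion.** The elimination paragraph is wrong as written. It makes the protocol's own fever endpoint, along with acute illness and antimicrobial use, a ground for removal from the study. It conflicts with the follow-up paragraph, the visit outline, the intussusception annex and the authors' reply in item 7. What it certainly costs, if followed, is later observation of the affected child. The documents do not establish loss of the recorded fever itself, or an excess loss on vaccine.

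The size is an illustration: 136 per arm falls to between 123 and 89 after two doses, with power about 4 to 18 points lower. It rests on fever alone, a constant independent rate of 5% to 19% per dose, and equal loss in the arms compared. At fever rates as low as those reported for RIX4414 the loss from fever would be smaller, but the contradiction would remain.

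**What to change.** Reconcile the elimination paragraph with the follow-up paragraph, the visit outline and the reply in item 7, by separating two questions the present sentence merges: whether a child is eligible for a further dose, and whether the child remains in the study. Suggested wording for the second:

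*A child who meets an exclusion criterion after the first dose remains in the study for all planned safety visits, sampling and the six-month follow-up, and is counted in the safety denominators. The event and its date are recorded.*

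The first question needs one consistent statement across the protocol. No view is taken here on which rule for further dosing is right.

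The cost is one paragraph of protocol text. No subjects or visits are added, because the visits are already planned for every child.
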